3.2.3 Secondary Endpoints

The first secondary endpoint is to observe successful conversion of at least one shockable rhythm with a salvo of up to five (5) shocks.

A shock is considered appropriate if the shock is delivered during a period where the subject is experiencing VF or a VT that is considered "life threatening" as defined in the CEC Charter and as adjudicated by the CEC. If multiple successful conversions occur in a single subject, conversions will be counted as separate events only if the rhythm returned to a non-shockable rhythm between conversions (i.e. the Jewel returns to Monitor Mode). All successful conversions will be included in the secondary endpoint analysis. All appropriate shocks and attempted conversions will be reviewed and adjudicated by the CEC and reported.

The second secondary endpoint is to observe a compliance rate of subjects wearing the Jewel of greater than 14.1 average hours per day during a prescription wear period.

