8.2.3 Time Period and Frequency for Event Assessment and Follow-Up

AEs and/or SAEs may come to the attention of study personnel during study follow-up phone calls, when the subject presents for office visits/medical care, or upon review of source documents by a study monitor.

All AEs, including local and systemic reactions not meeting the criteria for SAEs, will be captured on the appropriate CRF. Information to be collected includes event description, date of onset, clinician's assessment of severity, relationship to the Jewel, and resolution/stabilization of the event. All AEs occurring during the study must be documented appropriately, regardless of relationship. All AEs will be followed to adequate resolution or will be marked as ongoing at the time of study exit.

Any medical condition present at the time the subject is screened will be considered as baseline and not reported as an AE. However, if the subject's condition deteriorates at any time during the study, that condition's deterioration will be recorded as an AE.

Changes in severity of an AE will be documented to allow for an assessment of the duration of the event at each level of severity. All AEs will be characterized for severity when reported and, if ongoing, updates to the severity of any ongoing AEs will be assessed at subsequent visits.

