8.2.4 Adverse Event Reporting

AEs must be documented on a CRFs by site staff. It is the responsibility of the Investigator to ensure that all information is correct. When reporting any AEs or SAEs, the following information should be included:

- Description of event (including diagnosis)
- Onset date
- Severity
- Relationship to study device
- Action taken
- Outcome
- Duration / Resolution date

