10.1.6 Safety Oversight

All delivered shocks, both appropriate and inappropriate, will be reviewed and adjudicated by a CEC. The CEC will meet regularly, and may meet on-demand, as needed.

[contact]

Safety oversight will be provided under the direction of a DSMB composed of individuals with appropriate expertise, including interventional cardiology and/or electrophysiology. Members of the DSMB will be independent from the study conduct and free of conflict of interest, or measures will be in place to minimize perceived conflict of interest. The DSMB will meet regularly to assess safety and study conduct. The DSMB will operate under the rules of an approved charter that will be written and reviewed at the organizational meeting of the DSMB. At that time, each data element that the DSMB will assess will be clearly defined. The DSMB will provide its input to the Sponsor.

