It is anticipated that the Site and Sponsor may become aware of events of interest, but Jewel data are not available for the events due to mishandling, non-compliance with returning the device, inappropriate disposal, data overwriting, or data corruption. These events may include, for example, inappropriate shock delivery or appropriate shocks that may or may not have resulted in conversion of life-threatening VT or VF. Should any of these events of interest be reported by the subject or study site without the concurrent Jewel data available, the site shall provide the Sponsor and CEC with as much information regarding the event as possible. The CEC will review and adjudicate these situations on a case-by-case basis for inclusion in the endpoint analysis. Any such events will also be described.

As the Jewel collects some limited information on electrograms during wear-time, it is possible that cardiac events of interest may be captured by the Jewel. Data on incidental findings (i.e., arrhythmias not associated with a delivered or deferred shock) will not be provided to the investigation site team. However, if an event is adjudicated by the CEC and a cardiac rhythm of interest is observed, the CEC will inform the Investigator and provide the relevant supporting data.

Study Records Retention

Study documents should be retained for a minimum of two (2) years after the last approval of a marketing application or until at least two (2) years have elapsed since the formal discontinuation of clinical development of the Jewel. These documents should be retained for a longer period, however, if required by local regulations. No records will be destroyed without the written consent of the Sponsor. It is the responsibility of the Sponsor to inform the site when these documents no longer need to be retained.

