5.1. Primary Effectiveness Endpoints

All shocks during analyzable wear time will be recorded, centrally evaluated and adjudicated by the Clinical Events Committee (CEC), and reported.

The primary effectiveness endpoint is the rate of inappropriate shock. A one-sided upper 98% confidence limit will be calculated for the inappropriate shock rate per 100 patient-months at the final analysis. Specifically, an intercept-only Poisson regression model will be fit to the data. All wear times through the first inappropriate shock or through death or withdrawal or wear times for subjects without inappropriate shock, death, or withdrawal at the time of analysis will contribute to the Poisson regression model. The one-sided upper 98% confidence limit inappropriate shock rate will be calculated by taking the one-sided upper 98% confidence limit of the intercept parameter in the regression model. The null hypothesis will be rejected if the upper confidence limit on the inappropriate shock rate is less than 2.0.

The formal hypotheses are:

 H_0 : Inappropriate shock rate ≥ 2.0 per 100 patient-months H_a : Inappropriate shock rate < 2.0 per 100 patient-months

The analysis will be re-run on the per protocol analysis population if that population is different from the primary analysis population. Results of this analysis are strictly supportive.

Note that subjects experiencing an inappropriate shock will continue to be followed and accumulate wear time in order to collect data on the other endpoints of this trial.

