An analysis of all events that trigger the alarm cycle after three (3) segments of shockable rhythm (~24 seconds) during analyzable wear time will be performed. Each event will be categorized by the type of rhythm or event experienced. These categories of will be summarized in a frequency table showing the number and percentage of times each arrhythmia triggered the alarm cycle.

Quality of Life

A Quality of Life (QOL) measurement tool (EQ-5D-3L) will be used to quantify any impact that the Jewel has on a subjects QOL.

12.Protocol Deviations

Protocol deviations will be summarized in tabular form using the frequency and proportion of each type of deviation observed.

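### Protocol 10.1.8 leaves no assured route by which VT/VF that set off the alarm cycle, then ended without a shock or button press, reaches the site-completed AE/SAE record

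*Protocol*

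**What the plan says.** **Data flow to the site.** Protocol 10.1.8 (Jewel Device Data) states: "Data on incidental findings (i.e., arrhythmias not associated with a delivered or deferred shock) will not be provided to the investigation site team". The next sentence makes an exception: "if an event is adjudicated by the CEC and a cardiac rhythm of interest is observed, the CEC will inform the Investigator" and supply the supporting data.

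**Arrhythmia analysis.** SAP section 11 (Detection of Ventricular Arrhythmias), in line with protocol 3.2.4, takes every event that reaches the alarm trigger during analyzable wear time. The trigger is three segments of shockable rhythm, about 24 seconds. "Each event will be categorized by the type of rhythm or event experienced", and the results go into a frequency table of counts and percentages. Neither document says who does the categorising, or when.

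**AE record.** Protocol 8.2.3: "All AEs occurring during the study must be documented appropriately, regardless of relationship". Protocol 8.2.4: "AEs must be documented on a CRFs by site staff". Relatedness is judged by the Investigator (8.2.2). Protocol 9.4.2 and SAP 5.3 promise a summary of all AEs and SAEs, with the proportion of subjects affected.

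**CEC remit.** Protocol 10.1.6: "All delivered shocks, both appropriate and inappropriate, will be reviewed and adjudicated by a CEC". Protocol 3.2.3: "All appropriate shocks and attempted conversions will be reviewed and adjudicated by the CEC and reported". SAP 5.1: "All shocks during analyzable wear time will be recorded, centrally evaluated and adjudicated by the Clinical Events Committee (CEC), and reported". Protocol 10.1.8 adds events reported by a subject or site for which device data are unavailable.

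**The concern.** The sponsor's analysis will hold, for each alarm-cycle event, a rhythm category. Where that category is VT or VF and the episode ended by itself, the party that must complete the AE form is, by default, not given the data.

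In the protocol's vocabulary a shockable rhythm is one deemed life-threatening (6.1.2). An event that is life-threatening, in the sense of placing the subject at immediate risk of death, meets a seriousness criterion (8.2.1). The final report could then count such rhythms in one table while its AE and SAE tables omit them, and no one would have assessed them for seriousness or relatedness.

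This matters more in a single-arm study whose objective is to demonstrate safety (protocol 3.1 and 4.2). There is no comparator against which incomplete ascertainment might even out, so the AE/SAE summaries carry the general safety description.

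**Working it through.** There is no plan figure to reproduce. The check is whether an event can fall in the gap and, if so, whether any stated route takes it out again.

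1. **Can an episode alarm and end without a shock?** Yes. The alarm starts after about 24 s of shockable rhythm (SAP section 11). Protocol 6.1.2 puts the shock within 60 s of detection and makes it conditional on the rhythm continuing. The documents do not say when the 60 s begins. If it runs from rhythm onset, the window after the alarm is at most 60 − 24 = 36 s. If it runs from the alarm trigger, the window is at most 60 s. Either way, an episode can alarm, be logged and then stop.

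2. **Which of these does the non-disclosure sentence cover?** A button press makes the event a deferred shock (8.1.4), which the sentence does not withhold. A delivered shock is likewise outside it. What remains is alarm triggered, rhythm ended, no shock and no press. Episodes shorter than the trigger are also withheld, but SAP section 11 does not categorise them and they are not part of this point.

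3. **Does the analysis see them?** Yes. SAP section 11 includes all alarm-cycle events, with no condition that a shock follows. SAP 5.2 also has each shockable episode of VF or life-threatening VT described.

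4. **Is there a stated route to the AE form?**
   - *CEC exception (10.1.8).* It operates only on events the CEC adjudicates. The stated duties are shocks (protocol 3.2.1 and 10.1.6, SAP 5.1), attempted conversions (3.2.3) and reported events lacking device data (10.1.8). SAP 5.2 refers to the CEC's definition of life-threatening VT but does not send alarm-only episodes to the CEC.
   - *Monitor review of source documents (8.2.3).* Jewel records are source data (10.1.8), but no section says that monitors screen them for AEs. A monitor who found such an episode would still meet the non-disclosure sentence when passing it to the site.
   - *Sponsor or DSMB judgement of seriousness (8.2.1).* This grades an event. It does not create the site-completed form, and SAE reports run from site to sponsor (8.2.5).
   - *Subject report.* This is a real route. Sites ask about health status and AEs at Exchanges (8.1.4), and clinical events leading to visits or hospital care must be reported (8.2.9). However, the device-specific question concerns shocks deferred or received (8.1.4 and the Schedule of Activities), not alarms that stopped by themselves. A subject who slept through the episode may report nothing. One who fainted may report syncope without the rhythm.

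5. **Result.** Of the four routes, only subject report is both stated and workable, and it depends on symptoms or care-seeking. None starts from the device record.

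**The case against.** The strongest reply is that the sentence withholds device data, not the event. The site may record anything it learns from calls, visits, medical care or source review, so the two rules can coexist. That stands. A reader might infer that these episodes can never enter the AE record, or that 10.1.8 and 8.2.3 cannot both be obeyed. The documents do not support either inference.

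Second, the CEC sections say what the committee must review, not that it reviews nothing else. Investigators already receive a report on every delivered shock (10.1.8), so the exception would add little if it covered only those. The CEC Charter, cited in 3.2.3, and the DSMB charter (10.1.6) are not among the documents. This also stands in part: a route through the CEC is unassured, not shown to be absent.

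Third, the affected class is narrow. A conscious subject is told to press the buttons, and a persisting rhythm is shocked. Nor would every remaining episode be a reportable AE, since conditions present at screening count as baseline unless they deteriorate (8.2.3). That limits the number of events. It does not remove the need for someone at the site to make the assessment.

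Fourth, a reader might take the omission to hide arrhythmia caused by the device. The support for that is weak. Induction or acceleration of arrhythmia appears in 2.2.1 among the risks of the patient population. VT and VF do appear in the list of additional wearable-device risks, but the disputed events involve no shock, and 2.2.3 says the device otherwise runs at low current.

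Finally, the episodes are not lost to the report, because the arrhythmia table counts them. True, but that table carries no grading of seriousness or relatedness and does not inform the Investigator.

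**Conclusion.** The point holds as a gap created by a stated rule. As written, the non-disclosure sentence leaves no assured path from alarm-cycle VT/VF without a delivered or deferred shock to the AE/SAE record. The AE/SAE summaries can then disagree with the arrhythmia table, and the Investigator may not know of the episode.

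The size cannot be derived. The documents give no expected count, and zero is compatible with them. The three events anticipated in protocol 9.2 are successful conversions by shock, a different class, and cannot stand in. As a unit only, with the planned 290 subjects as denominator, each omitted subject would lower a subject-level proportion by 1/290 = 0.3 percentage points.

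The primary effectiveness endpoint (inappropriate shocks) and the primary safety endpoint (cutaneous ADEs leading to withdrawal) are unaffected.

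The conclusion assumes that the CEC and DSMB charters do not already bring in alarm-only episodes. If either does, the protocol need only say so. It also does not suppose that the sponsor knows of these events in real time. Compliance data are reviewed after device return (6.4), device records are extracted after the prescription period or device use (10.1.8), and SAP section 11 sets no timing.

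**What to change.** Reconcile protocol 10.1.8 with 8.2.3, 8.2.4 and SAP section 11:

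- Limit the non-disclosure sentence in 10.1.8 to rhythms that did not trigger the alarm cycle.
- State that alarm-cycle events categorised as VT or VF, with no delivered or deferred shock, go to the Investigator as an AE query, directly or through the CEC, for assessment of seriousness and relatedness.
- List these events for the DSMB.
- Name in SAP section 11 who categorises alarm-cycle events and when.

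The cost is one amended protocol sentence, a short SAP addition and a few extra queries; the categorisation is already planned. The drawback is timing: where data are read only after device return, some queries will arrive late and will serve completeness of the record more than prompt awareness. The change concerns reporting only and alters no aspect of device use or patient management.

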10.1.9 Protocol Deviations

A protocol deviation is any change, divergence, or departure from the study design or procedures defined in the protocol. The deviation may be either on the part of the subject, the Investigator, or the site staff. As a result of repeated deviations, corrective actions are to be developed and implemented promptly.

Major protocol deviations are a subset of protocol deviations that might significantly affect the completeness, accuracy, and/or reliability of the study data or that might significantly affect a subject's rights, safety, or well-being. For example, major protocol deviations include enrolling subjects in violation of key eligibility criteria, failing to properly obtain informed consent, or failing to collect data necessary to interpret primary endpoints, as this may compromise the scientific value of the trial.

It is the responsibility of the Investigator to use continuous vigilance to identify and report all protocol deviations within seven (7) working days of identification of the deviation. All deviations must be addressed in study source documents and reported to the Sponsor. Protocol deviations must be sent to the reviewing IRB per their policies. The Investigator is responsible for knowing and adhering to the reviewing IRB requirements.

10.1.10 Publication and Data Sharing Policy

Study outcomes will be reported in a peer reviewed journal, as appropriate. Authorship and publication shall be according to the Sponsor's policies. The study will be posted on ClinicalTrials.gov and results will be posted on ClinicalTrials.gov as required.

10.1.11 Conflict of Interest Policy

All Investigators shall provide the Sponsor with a Financial Disclosure Form prior to initiating any study activities at their sites, at the conclusion of the study, and one year after the study ends.

PR-2053 Rev. E

Further, during the course of the study, Investigators should make best efforts to disclose any new conflicts (both actual and perceived) to the Sponsor in a timely manner. Any actual or perceived conflicts of interest shall be reviewed by the Sponsor and shall be disclosed and managed as appropriate.

10.2 Abbreviations

AE	Adverse Event
AE	Automated External Defibrillator
CABG	
	Coronary Artery Bypass Grafting
CEC	Clinical Events Committee
CFR	Code of Federal Regulations
CMP	Clinical Monitoring Plan
CRF	Case Report Form
DMP	Data Management Plan
DSMB	Data Safety Monitoring Board
ECG	Electrocardiogram
EP	Electrophysiology
FDA	Food and Drug Administration
ICD	Implantable Cardioverter Defibrillator
IDE	Investigational Device Exemption
IEC	International Electrotechnical Commission
IRB	Institutional Review Board
LN	Lot Number
LVEF	Left Ventricular Ejection Fraction
MI	Myocardial Infarction
MRI	Magnetic Resonance Imaging
PCI	Percutaneous Coronary Intervention
PI	Principal Investigator
P-WCD	Patch – Wearable Cardioverter Defibrillator
SAP	Statistical Analysis Plan
SAE	Serious Adverse Event
SCA	Sudden Cardiac Arrest
SCD	Sudden Cardiac Death
SN	Serial Number
TTI	Transthoracic Impedance
US	United States
VF	Ventricular Fibrillation
VT	Ventricular Tachycardia
WCD	Wearable Cardioverter Defibrillator

10.3 Protocol Amendment History

Revision	Date	Comment
А	28 Mar 2018	Initial Release
В	12 Jun 2018	Updates per FDA feedback. -Primary Safety and Effectiveness Endpoint revision -Additions to Exclusion Criteria -General Clarifications
С	03 Aug 2018	Section 9.4.5 was inadvertently not updated in Rev B. Rev C updated this section to remove reference to a performance goal and freedom from inappropriate shock.
D	16 Apr 2021	Updates to revise device used in study; adjust study processes to reflect Durable Medical Equipment nature of the ES-2; include allowances for the COVID-19/SARS-CoV-2 pandemic; update Section 9.2 to match the Statistical Analysis Plan, include Subject requests for Sponsor contact.
E	22 October 2021	Revised Primary Effectiveness endpoint and incorporated an interim analysis at 179 analyzable subjects to allow for early stopping for safety and effectiveness.

While the Implantable Cardioverter Defibrillator (ICD) is typically implanted for long-term prevention of SCA in high-risk populations, there are temporary periods of time when ICD implantation is commonly deferred. Examples include the initial 40-days after myocardial infarction (MI), the initial 90-days after percutaneous coronary intervention (PCI) or coronary artery bypass grafting (CABG), or after ICD explantation. The Wearable Cardioverter Defibrillator (WCD) has become a viable option to treat these temporary periods of elevated risk for SCA. Patients typically are prescribed to wear a WCD 24 hours a day, 7 days a week for 40 to 90 days or longer until a medical decision is made on whether to implant an ICD.

The Jewel Patch Wearable Cardioverter Defibrillator (P-WCD) is a Wearable Cardioverter Defibrillator that monitors patients at risk for SCA and provides a therapeutic shock if needed. It is intended to be worn at home or in hospital during temporary periods of time when ICD implantation is commonly deferred.

2. Study Design

This study is a multi-center, prospective, single-arm, non-randomized, unblinded evaluation of the Jewel P-WCD in adult subjects at risk for sudden cardiac arrest, who are not candidates for or who refuse an implanted defibrillator. This trial has one interim analysis scheduled after 179 subjects have completed their prescription wear time.

A subject is considered to have completed the study when his or her physician-determined prescription period has ended. The study Exit Visit will be performed at this time. Subject prescription periods may be altered during the course of the study at physician discretion. The end of the study is defined as when the last subject exits the study.

¹ Sudden Cardiac Death (Sudden Cardiac Arrest) | Cleveland Clinic [Internet]. [cited 2018 Feb 19]. Available from: https://my.clevelandclinic.org/health/diseases/17522-sudden-cardiac-death-sudden-cardiac-arrest

3. Analysis Populations

3.1. Primary Analysis Population

All subjects with analyzable wear times following initial Jewel enrollment will be included in the analysis population for the primary effectiveness endpoint. Analyzable wear time is defined as beginning 12-hours after the date and time the first Jewel applied to the subject's body transitions to Monitor Mode to when the last Jewel worn by the subject transitioned to Off Body Mode. Periods of removal time as identified by timestamped transitions between modes, periods of removal time as attested to by a subject or health care provider and confirmed by electrocardiographic data, and periods of time in which there are missing data (e.g. due to unreturned or damaged devices) will be excluded.

